Amendment 08	22-Mar-2017	In order to further explore an emerging efficacy signal, additional patients with previously untreated metastatic melanoma (ie, no prior systemic anticancer therapy for unresectable or metastatic melanoma) subjects with PD-L1 negative tumors (<1%) will be enrolled under this amendment.
Revised Protocol 05	09-May-2016	Incorporates Amendment 06 and Administrative Letters 04 and 05
Amendment 06	09-May-2016	To include a cohort of NSCLC and melanoma subjects who have relapsed or are refractory to prior anti-PD-1/anti-PD-L1 therapy.
Administrative Letter 05	01-Jun-2016	To clarify application to new cohort of subjects with NSCLC and melanoma who have relapsed or are refractory to prior anti-PD-1/anti-PD-L1) therapy and exception for NSCLC and MEL subjects enrolling in the expansion cohorts where prior anti-PD-1 or anti-PD-L1 therapies are specifically required.
Administrative Letter 04	19-Jan-2016	Change in MM
Revised Protocol 04	22-Dec-2015	Incorporates Amendment 05
Amendment 05	22-Dec-2015	To expand the study population for cohort expansion to include subjects with follicular lymphoma and to further differentiate subjects with non-small-cell lung cancer into two separate groups (those with no prior anti PD-1/anti-PD-L1 therapy and those who have relapsed or are refractory to prior anti-PD-1/anti-PD-L1).
Revised Protocol 03	30-Aug-2015	Incorporates Amendment 04 and Administrative Letter 03
Amendment 04	30-Aug-2015	Discontinue enrollment into Cohorts A, B, C, D. Implement an update to exclusion Criteria
Admin Letter 03	26-Aug-2015	Discontinue enrollment into Cohorts A, B, C, D during cohort expansion
Revised Protocol 02	29-Jun-2015	Incorporates Amendment 03
Amendment 03	29-Jun-2015	To implement a change in duration to combination therapy and use of flat dosing for subjects enrolled following approval of Revised Protocol 02
Revised Protocol 01	06-Mar-2015	Incorporate Amendment 02
Amendment 02	06-Mar-2015	To implement changes to inclusion/exclusion criteria, clarify requirements and assessments for treatment beyond disease progression and criteria for allowing treatment to resume after a dose delay due to toxicity, add time and events schedules for subjects eligible for retreatment, and clarify PK sampling and biomarker assessments.

Document	Date of Issue	Summary of Change
Adm Letter 02	21-Oct-2014	To correct a typographical error and to clarify that drug preparation, storage, handling and dispensing of nivolumab is contained in the Investigator Brochure and/or pharmacy reference sheets, and the interval between end of nivolumab dose and beginning of urelumab dose.
Adm Letter 01	30-Sep-2014	To correct PK sample time points and clarify the expected time points for vital signs and observation period of subjects post-dosing.
Original Protocol	10-Jun-2014	Not applicable

SYNOPSIS

Clinical Protocol CA186107

Protocol Title: A Phase 1/2 Dose Escalation and Cohort Expansion Study of the Safety and Tolerability of Urelumab Administered in Combination with Nivolumab in Advanced /Metastatic Solid Tumors and B Cell Non-Hodgkin's Lymphoma

Investigational Product(s), Dose and Mode of Administration, Duration of Treatment with Investigational Product(s): Each subject will be administered intravenous (IV) doses of urelumab (BMS-663513) every 4 weeks and nivolumab (BMS-936558) every 2 weeks, for up to 48 weeks of study therapy.

Retreatment with the combination at the dose and regimen assigned at study entry, within 12 months of last treatment with study drug, may be permitted after discussion and agreement with the BMS Medical Monitor.

Study Phase: 1/2

Research Hypothesis:

It is anticipated that the combination of an anti-CD137 (urelumab) and an anti PD-1 antibody (nivolumab) will demonstrate adequate safety and tolerability at pharmacologically relevant doses, so as to permit further clinical testing. There is no formal primary research hypothesis for this study to be statistically tested.

Objectives:

Primary Objective: To assess the safety and tolerability of urelumab given in combination with nivolumab and to identify dose limiting toxicities (DLTs) and the maximally tolerated dose (MTD) of the combination, in subjects with advanced (metastatic and/or unresectable) solid tumors and B cell lymphomas.

Secondary Objectives:

- To assess the preliminary anti-tumor activity of the combination of urelumab and nivolumab in subjects with advanced solid tumors and B cell lymphomas.
- To characterize the pharmacokinetics (PK) of urelumab and nivolumab when co-administered.
- To monitor immunogenicity of urelumab and nivolumab administered as combination therapy.

[figure not shown]
[REDACTED]
[REDACTED]
[REDACTED]
[REDACTED].

Study Design:

This is a phase 1/2 open label study. The first phase of the study will consist of a dose escalation assessment of the safety and tolerability of urelumab administered with nivolumab in subjects with advanced solid tumors or B-cell non-Hodgkin's lymphoma (NHL). The second phase of the study will include a 2-stage cohort expansion in multiple tumor types (melanoma, non-small cell lung cancer, head and neck squamous cell carcinoma, diffuse large B cell lymphoma, and follicular lymphoma) at the maximally tolerated dose (MTD), highest administered dose (HAD), or at an alternative dose/regimen as determined by the investigators and the sponsor and outlined in the Study Population section ([Section 3.3](#)).

The study design schema is outlined below in Figure 1:

Figure 1: **Study Design Schema**

CR = complete response; PR = partial response; SD = stable disease; PD = progressive disease

Subjects will complete up to four periods of the study:

Screening (up to 28 days):

Subjects will sign consent and be evaluated for study eligibility.

Treatment (up to a maximum of 6 cycles of study therapy):

The Treatment Period will consist of up to 6 treatment cycles. Each cycle is 8 weeks for a total of 48 weeks. Nivolumab will be given every 2 weeks up to 48 weeks. Urelumab will be given every 4 weeks up to 48 weeks. On days where both study drugs are given, nivolumab will be given first followed by urelumab.

Clinical/Safety Follow-up (100 days following study drug discontinuation):

Subjects that discontinue the treatment phase will enter the Clinical/Safety Follow-up period, with visits scheduled on days 30, 60 and 100 to monitor for adverse events.

Survival/Long-Term Follow-up (survival will last up to 3 years following the first dose of study drug):

The duration of survival follow-up will be up to 3 years following the first dose of study drug. Subjects who discontinue study drug with ongoing SD, PR, or CR will continue to have tumor assessments completed every

12 weeks for the first year after discontinuation of study drug, and then continue to receive scans as per standard of care guidelines for follow-up or at a minimum of every 6 months for up to 3 years following the first dose of study drug, or until disease progression or withdrawal of consent. Subjects in the Survival/Long-term Follow-up period who have progression of disease will be allowed to receive tumor directed therapy as required.

Re-treatment with the combination at the dose and regimen assigned at study entry, within 12 months of last dose of study drug, may be permitted after discussion and agreement with the BMS Medical Monitor, provided that the subject continues to meet the re-treatment eligibility criteria. These subjects will complete up to 4 additional periods of the study: screening, treatment, clinical follow-up, and survival/long-term follow-up.

Dose Escalation:

A 3+3+3 design will be used to assess the safety of urelumab given in combination with nivolumab. The cohorts for dose escalation are provided in Table 1. Potential alternate cohorts are provided in [Table 3](#). The Dose Limiting Toxicity (DLT) observation period will last for 8 weeks following the first dose of study medication. The DLT evaluation period is defined as 8 weeks after administration of the first combination dose of nivolumab and urelumab, and includes subjects who have had administration of at least one dose of nivolumab monotherapy during this interval. This interval is based upon inclusion of the earliest times to onset of clinically significant adverse events attributed to study drug, and also allows for a substantial amount of time for unexpected toxicities related to dosing regimen to emerge.

Approximately three subjects will be treated initially at each dose regimen. In order to assure sufficient evaluable subjects per cohort an additional subject may be added to a cohort (ie, enroll a fourth subject in a cohort of 3).

Note: Should this action be taken, cohort tolerability assessment and subsequent dose escalation, if indicated, will occur when the minimum number of subjects required to assess tolerability have completed the 8 week DLT period. However, if any additional subject experiences an event that would, per protocol, result in either cohort expansion or the halting of dose escalation, the escalation rules as defined below in [Table 2](#) will be followed.

Table 1: Doses/Regimens During Dose Escalation			
Cohort Number	Total Subjects^a	urelumab	nivolumab^b
1	n = approximately 3-9	3 mg IV every 4 weeks	3 mg/kg or 240 mg IV every 2 weeks
2	n = approximately 3-9	8 mg IV every 4 weeks	3 mg/kg or 240 mg IV every 2 weeks
Total	n = approximately 6-18		

^a 3-9 subjects will be enrolled during dose escalation. Additional subjects may be added for a total of up to 12 subjects per dose level

^b Nivolumab 3 mg/kg will be administered for subjects enrolled prior to Revised Protocol 02. Nivolumab 240 mg flat dose administered for subjects enrolled after Revised Protocol 02

After dose escalation to the next cohort, 3-9 additional subjects may be enrolled in any previously tolerated dose level (original 3-9 subjects from dose escalation plus additional subjects required to have a total cohort size of 12). If the rate of DLTs exceeds 33% in a given treatment regimen; the findings will be discussed and further enrollment may be interrupted for that specific treatment regimen and tumor type. If one of the planned dose cohorts is determined to exceed the MTD, and/or based on ongoing safety/tolerability experience through the dose escalation phase of the study, an alternate dose escalation schema as outlined in [Table 3](#) may be explored in consultation and agreement between the Sponsor and investigators.

Sentinel Subject: During dose escalation, the first subject in each cohort will receive C1D1 (eg, the first dose of study drugs) and be observed for 3 weeks such that one combination dose followed by one nivolumab dose are administered before additional subjects in the cohort receive the first dose of study drug (ie, C1D1).

Dose Escalation Rules:

Table 2 outlines the decision rules for dose escalation based on the number of subjects and observed DLTs. No intra-subject dose escalation or reduction is allowed. Subjects who withdraw from the study during the DLT period for reasons other than a DLT may be replaced within the same dose level/regimen. Dose escalation will be based on the number of dose limiting toxicities (DLTs) experienced during the DLT observation period

If dose escalation is terminated, then the dose or dose regimen below that which invoked the stopping rule will be declared the MTD.

Table 2: Decision Rules During Dose Escalation

Number of Evaluable Subjects/ Cohort	3-4			6-8			9-12	
Total Number of Observed DLTs	0	1	2 or more	1	2	3 or more	2	3 or more
Decision Rule	Dose Escalate	Enroll additional subjects at in cohort to reach at least 6 subjects	Dose exceeds MTD	Dose Escalate	Enroll additional subjects at in cohort to reach at least 9 subjects	Dose exceeds MTD	Dose Escalate	Dose exceeds MTD

If either Cohort 1 or Cohort 2 exceeds the MTD, alternate treatment regimens may be explored during dose escalation or cohort expansion (listed in Table 3).

Table 3: Alternate Treatment Regimens

Cohort	urelumab	nivolumab ^a
A ^b	8 mg IV every 8 weeks	3 mg/kg or 240 mg IV every 2 weeks
B ^b	8 mg IV every 8 weeks	1 mg/kg or 80 mg IV every 2 weeks
C	3 mg IV every 4 weeks	1 mg/kg or 80 mg IV every 2 weeks
D ^b	3 mg IV every 8 weeks	3 mg/kg or 240 mg IV every 2 weeks

^a Nivolumab 1 mg/kg or 3 mg/kg will be administered for subjects enrolled prior to Revised Protocol 02. Nivolumab 80 mg or 240 mg flat dose administered for subjects enrolled after Revised Protocol 02

^b Treatment regimen not applicable following Revised Protocol 03.

All available clinical and laboratory data observed during dose escalation will be reviewed to determine the alternative treatment regimen listed in Table 3 to be evaluated. The nature, time of onset, and time to resolution of DLTs observed will be reviewed in the context of the current safety data from the respective urelumab and

nivolumab trials. After review of this data, and after consultation between the investigators and the sponsor, the identified alternative treatment regimens may be evaluated.

Cohort Expansion:

The purpose of the cohort expansions is to gather additional safety, tolerability, preliminary efficacy and pharmacodynamic information regarding the combination of urelumab and nivolumab. Once the MTD of combined administration of urelumab and nivolumab has been defined, cohort expansions will be initiated.

Expansion cohorts will follow a 2-stage design as defined below in Table 4:

Table 4: Cohort Expansion

Tumor Types	Stage 1 Expansion	Stage 2 Expansion
Non-small Cell Lung Cancer (NSCLC)	Up to approximately 20 subjects at MTD or HAD	Up to approximately 20 subjects
Melanoma (MEL)	Up to approximately 20 subjects at MTD or HAD	Up to approximately 20 subjects
Head and Neck Squamous Cell Carcinoma (SCCHN)	Up to approximately 20 subjects at MTD or HAD	Up to approximately 20 subjects
Diffuse Large B Cell Lymphoma (DLBCL)	Up to approximately 20 subjects at MTD or HAD	Up to approximately 20 subjects
NSCLC (progressive or recurrent disease during or after anti-PD-1/anti-PD-L1 therapy)	Up to approximately 20 subjects at MTD or HAD	Up to approximately 20 subjects
Follicular Lymphoma (FL)	Up to approximately 20 subjects at MTD or HAD	Up to approximately 20 subjects
Melanoma (progressive or recurrent disease during or after an anti-PD-1/anti-PD-L1 containing treatment regimen)	Up to approximately 20 subjects at MTD or HAD	Up to approximately 20 subjects
Melanoma PD-L1 negative	Up to approximately 50 subjects at MTD or HAD	

Stage 1 of the expansion phase will treat 20 subjects per tumor type at the MTD and HAD as identified during dose escalation followed by Stage 2: continued enrollment of up to approximately 20 additional subjects (total of 40 subjects per tumor type) (Stage 2) to obtain additional safety/efficacy data for the combination.

The safety, tolerability, and preliminary efficacy data from Stage 1 of the cohort expansion will be evaluated per tumor type and discussed by the sponsor with investigators prior to enrolling 20 additional patients during Stage 2.

Efficacy criteria for moving to Stage 2:

A minimum of 4 out of 20 subjects should demonstrate an objective response to study therapy. In general, if 0 to 3 responses are observed in a given tumor specific cohort during Stage 1 of cohort expansion, Stage 2 will not be enrolled for that tumor type. Please note: Ongoing assessment of data from initial 20 patients may be used to consider additional enrollment in that tumor type at a later date (to consider the possibility of delayed responses).

An additional 50 treatment naïve PD-L1 negative melanoma subjects will be treated at MTD/HAD to further evaluate if there is an efficacy signal in this population. Additional subjects may be enrolled and treated so as to accrue a minimum of 50 evaluable subjects with at least 2 on treatment scans.

Safety criteria for moving to Stage 2:

If the rate of DLTs exceeds 33% in a given tumor type; the findings will be discussed by sponsor with investigators and further enrollment may be interrupted for that specific tumor type.

Safety data from subjects enrolled in Stage 1 of the expansion phase will be reviewed by BMS medical and safety teams, and discussed with and endorsed by participating investigators, prior to moving to Stage 2 of cohort expansion.

If the efficacy and safety data from a given tumor type meet the minimum criteria for moving forward, approximately 20 additional subjects will be enrolled during Stage 2 of cohort expansion. The evaluation of data from Stage 1 and the decision to begin Stage 2 of the expansion phase of the study can be made up to one year following completion of the enrollment of Stage 1 for each individual tumor type.

Dose Limiting Toxicity: DLTs are defined in [Section 4.5.2](#). The incidence of DLTs which occur within 8 weeks following the start of study therapy will guide dose escalation decisions. Adverse events will be graded according to the National Cancer Institute (NCI) Common Terminology Criteria for Adverse Events version 4.0 (CTCAEv4).

For the purposes of subject management, drug-related AEs occurring at any time which meet the DLT definition will lead to dose interruption and or permanent discontinuation of study drug as defined in [Sections 4.5.5](#) and [4.5.7](#).

Duration of Study: The total time on study for any individual subject is expected to be approximately 3.1 years. The total duration of the study is expected to be 4.5 years from the time of the first visit of the first subject to the required survival follow-up of the last subject enrolled.

Number of Subjects: Up to approximately 260 subjects will be dosed.

Study Population:

Subjects at least 18 years old, who have histologic confirmation of a solid malignancy or B-cell NHL that is advanced (metastatic and/or unresectable), with measurable disease will be eligible to participate in the study.

For Dose Escalation: Subjects with any solid tumor type (with the exception of primary central nervous system tumors) and B-cell NHL are eligible to enroll.

For Cohort Expansion: Subjects must have one of the following tumor types to be eligible: NSCLC; MEL, SCCHN, DLBCL, or FL.

- ◆ A fresh biopsy is required to determine PD-L1 status prior to treatment into the PD-L1 negative, treatment-naive melanoma cohort.

Study Drug: includes both Investigational [Medicinal] Products (IP/IMP) and Non-investigational [Medicinal] Products (Non-IP/Non-IMP) as listed:

Study Drug for CA186107		
Medication	Potency	IP/Non-IP
Urelumab (BMS-663513)	5 mg/mL	IP
Nivolumab (BMS-936558)	10 mg/mL	IP

Study Assessments:

Safety Outcome Measures: Safety assessments will be based on medical review of adverse event reports and the results of vital sign measurements, ECGs, physical examinations, and clinical laboratory tests. The incidence of observed adverse events will be tabulated and reviewed for potential significance and clinical importance. Adverse events will be assessed continuously during the study and for 100 days after the last treatment. Both AEs and laboratory tests will be graded using the NCI CTCAEv4.

Efficacy Measures:

- In solid tumor patients, disease assessment with computed tomography (CT) and/or magnetic resonance imaging (MRI), as appropriate, will be performed at baseline and every 8 weeks until confirmed disease progression, at the completion of follow-up, or until subjects withdraw from the study. Tumor responses will be derived for appropriate populations of subjects as defined by RECIST v1.1 based on recorded tumor measurements (see [Appendix 1](#)).
- For lymphomas, the primary efficacy assessment is objective response rate (ORR), defined as a subject achieving either a partial remission (PR) or complete remission (CR) according to the revised International Working Group Criteria for non-Hodgkin Lymphoma (Revised Response Criteria for Malignant Lymphoma, Cheson BD, J Clin Onc,2007 Feb 10;25(5):579-86. Epub 2007 Jan 22, [\[Appendix 2\]](#)). The primary efficacy assessment, along with the secondary endpoints of duration of OR, complete remission rate (CR), and progression free survival (PFS) will be performed based on investigators assessments. Subjects will be assessed for response by imaging (spiral CT/MRI) beginning at week 8 and follow the schedule shown in [Table 5.1-2](#) and [Table 5.1-3](#) until disease progression. A PET scan is required to confirm CR. Subjects eligible for re-treatment will be assessed for response by imaging (spiral CT/MRI) beginning at week 8 and follow the schedule shown in [Table 5.1-5](#) and [Table 5.1-6](#) until disease progression.
- At the sponsor's discretion, scans and measurements may be collected and reviewed by independent radiologists at a later date, or at any time during the study.

Pharmacokinetic Measures: The nivolumab pharmacokinetic concentrations will be measured at specified time points to derive the PK parameters (Ceoinf, Ctrough, Cmax, Tmax, AUC [0-T], AUC[TAU]). Pharmacokinetic serum concentrations of urelumab will be measured at specified time points to derive PK parameters (Ceoinf, Cmax, Ctrough, Tmax, AUC[0-T], AUC[TAU]).

Immunogenicity Measures: Serum samples to evaluate development of positive anti-drug antibody (ADA) response to urelumab and nivolumab will be collected at specified time points.

Biomarker Measures: The sample collection and biomarker assessment strategy is designed to address the key questions listed below regarding the actions of urelumab and nivolumab and the simultaneous modulation of the innate and adaptive immune systems.

- Does concurrent blockade of the PD-1 pathway and costimulation with anti-CD137 agonistic antibody affect aspects of innate and adaptive immunity that lead to enhancement of clinical activity (versus activity previously observed using either agent alone)?
- Are there pre-treatment markers expressed in blood or tumor tissue (eg, PD-L1; CD137) that associate with clinical outcomes?
- Does the combination of CD137 agonism with PD-1 blockade enhance anti-PD-1- and/or anti-CD137-mediated pharmacodynamic effects (versus effects previously observed using either agent alone)?

- Separate whole blood samples (PAXgene) will be obtained at baseline and at multiple times during treatment to monitor pharmacodynamic changes in expression of immunoregulatory genes including immunoglobulins, interferon-inducible genes, and genes associated with major immune cell subtypes.

Whole Blood - for PBMC-based cytometry: Cytometry will be used to assess baseline and serial on treatment alterations in composition/activation status of lymphocyte subsets present in peripheral blood mononuclear cell preparations (PBMCs).

Serum: To understand the prevalence of circulating proteins and the impact they may have on the clinical activity and/or safety of nivolumab-urelumab treatment, the protein concentrations of a panel of cytokines, chemokines, and other relevant immunomodulatory, serum-soluble factors will be investigated by ELISA and/or other relevant multiplex-based protein assay methods.

Statistical Considerations:

Sample Size Determination:

Dose escalation: As this is a Phase 1/2 dose escalation trial, the sample size at each dose cannot be determined exactly, as it depends on the number of observed toxicities. Approximately 3 to 9 subjects are expected to be treated during dose escalation in each cohort, and up to 12 subjects may be dosed at selected cohorts.

Cohort Expansion:

Stage 1: During Stage 1 of the cohort expansion, approximately 20 subjects in each tumor type will be treated at the MTD/HAD dose level and schedule. With a sample size of approximately 20 subjects in each treatment regimen, it is intended to provide a general picture of the safety of each regimen. For example, if a low grade adverse event were observed in 3 or fewer patients, the 90% 1-sided upper confidence interval would be 30%.

Stage 2: During Stage 2 of cohort expansion, up to approximately 20 additional subjects will be treated in each tumor type. This will allow for further establishment of the safety profile of the combination and a preliminary assessment of efficacy. A total of 40 subjects (20 from Stage 1 and 20 from Stage 2) is based on achieving a higher precision. If in a cohort of 40 subjects 12, 15, or 18 responses are observed, then the lower limit of the one-sided 90% exact binomial CI for the ORR is 20%, 27%, and 34% respectively. These calculations are based on the Clopper-Pearson method for exact confidence intervals. If the true ORR in a tumor type is 50%, then with 40 subjects in a tumor type there is 96% chance of observing at least 15 responses, and 87% chance of observing at least 17 responses, and there is 8% chance of observing 15 or fewer responses (false negative rate).

[figure not shown]
An additional 50 treatment naïve PD-L1 negative melanoma subjects will be treated at MTD/HAD to further evaluate if there is an efficacy signal in this population. Additional subjects may be enrolled and treated so as to accrue a minimum of 50 evaluable subjects with at least 2 on treatment scans. These 50 PD-L1 negative melanoma patients will be combined for analysis with approximately 18 PD-L1 negative melanoma patients from Cohort 2 for a total of 68 PD-L1 negative melanoma patients. Assuming an ORR of approximately 56%, a minimum of 38/68 responders would provide a 95% Clopper-Pearson confidence interval with a lower limit above 42%.

Endpoints:

Primary Endpoint: Safety as measured by the rate of adverse events (AEs) and serious adverse events (SAEs), is the primary endpoint of this Phase 1/2 study. All subjects who receive at least one (full or partial) dose of urelumab or nivolumab will be evaluated for safety during treatment and for up to 100 days in follow-up.

Secondary Endpoints:

- **Efficacy:** Best overall response (BOR), objective response rate (ORR), duration of response, and progression free survival rate (PFSR) will be assessed based on RECIST v1.1 in subjects with solid tumors, and based on investigator assessment per revised IWG criteria in subjects with lymphomas.
- **Pharmacokinetics:** Urelumab and nivolumab maximum concentration (Cmax [μ g/mL]), end of infusion concentration (Ceoinf), time to maximum concentration (Tmax [hr]) trough concentration (Ctrough [μ g/mL]) and area under the curve (AUC[0-T] and AUC[TAU] [μ g.hr/mL]) will be evaluated using non-compartmental analysis in all treated subjects with adequate serum concentration data.
- **Immunogenicity:** Occurrence of specific ADA to urelumab and nivolumab will be determined.

Statistical Analysis:

Safety: All recorded adverse events will be listed and tabulated by system organ class, preferred term, tumor type, and treatment arm. The most current version of MedDRA will be used for coding. Vital signs and clinical laboratory test results will be listed and summarized by tumor type and treatment arm. Any significant physical examination findings and results of clinical laboratory tests will be listed. ECG results will be evaluated by the investigator; clinically significant abnormalities will be listed.

Pharmacokinetics: Summary statistics will be tabulated for the pharmacokinetic parameters by tumor type, dose, regimen, study day and time on urelumab PK subjects and nivolumab PK subjects where data is available. This data may also be pooled with other datasets for population PK analysis which will be part of a separate report.

Immunogenicity Analyses: A listing will be provided of all available immunogenicity data. Additionally, a listing of immunogenicity data from those subjects with at least one positive ADA at any time point will be provided. The frequency of subjects with at least one positive ADA assessment, and frequency of subjects who develop ADA after a negative baseline assessment will be provided. To examine the potential relationship between immunogenicity and safety, the frequency and type of AEs of special interest may be examined by overall immunogenicity status.

Efficacy Analyses: Individual BOR, duration of response and PFS will be listed using RECIST v1.1 criteria in solid tumors and investigator assessed revised IWG criteria in lymphomas. BOR outcomes will be tabulated by tumor type and treatment arm. The ORR and PFS rate (eg, at 24 weeks) and the corresponding confidence interval will be provided by tumor type and treatment. The duration of response and PFS will be estimated by Kaplan-Meier methodology by tumor type, depending on data availability. PFS rates at 24 weeks will be similarly estimated, based on Kaplan-Meier methodology. Presentations of efficacy will include subjects in cohort expansion and subjects in dose escalation matching those in cohort expansion by tumor type and treatment. Individual changes in the tumor burden over time will be presented graphically within a tumor type. Landmark overall survival will also be assessed as part of exploratory efficacy analysis, by Kaplan-Meier plots and medians for each tumor type.

[REDACTED]

[REDACTED]

[REDACTED]

[REDACTED]

[REDACTED]

TABLE OF CONTENTS

TITLE PAGE	
DOCUMENT HISTORY	
SYNOPSIS	
TABLE OF CONTENTS	
[REDACTED]	
1.2 Research Hypothesis	34
1.3 Objectives(s)	34
1.3.1 Primary Objectives	34
1.3.2 Secondary Objectives	34
[REDACTED]	
1.4 Product Development Background	35
1.4.1 Pharmacology	35
1.4.2 Toxicity	35
1.4.3 Clinical Pharmacology and Safety	36
1.4.3.1 Pharmacokinetics of urelumab and nivolumab	38
1.4.4 Immunogenicity of Urelumab	39
1.5 Overall Risk/Benefit Assessment	39
2 ETHICAL CONSIDERATIONS	41
2.1 Good Clinical Practice	41
2.2 Institutional Review Board/Independent Ethics Committee	42
2.3 Informed Consent	42
3 INVESTIGATIONAL PLAN	43
3.1 Study Design and Duration	43
3.1.1 Screening Period	43
3.1.2 Treatment Period	43
3.1.3 Clinical/Safety Follow-up	44
3.1.4 Survival/Long-Term Follow-up	44
3.1.5 Dose Escalation	45
3.1.6 Cohort Expansion	48
3.1.6.1 Stage 1 Cohort Expansion	49
3.1.6.2 Stage 2 Cohort Expansion	50
3.2 Post Study Access to Therapy	50
3.3 Study Population	50
3.3.1 Inclusion Criteria	50
3.3.2 Exclusion Criteria	58
3.3.3 Women of Childbearing Potential	61
[REDACTED]	

3.5 Discontinuation of Subjects from Treatment.....	63
3.5.1 Treatment Beyond Disease Progression	64
3.5.1.1 Discontinuation due to further progression	64
3.5.1.2 Assessment schedule for the subjects with post-progression treatment	65
3.6 Post Study Drug Follow-up	65
3.6.1 Withdrawal of Consent	65
3.6.2 Lost to Follow-Up	65

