Preliminary data in 138 patients treated with urelumab and nivolumab as of the clinical cutoff date of 30-Sep-2016, revealed that the most frequent TRAE was fatigue (31%); grade 3/4 ALT/AST elevations (2%/2%) and TRAEs leading to discontinuation (6%) were infrequent. No treatment-related deaths were reported. Twenty-five of 124 evaluable patients treated with the combination had objective responses (melanoma, n=23; SCCHN, n=1, NSCLC, n=1). The ORR in melanoma was 50% (23/46) including 9/18 of subjects with PD-L1 negative tumors by IHC.

There remains a significant unmet need for curative options in the tumor types being evaluated in this study including PD-L1 negative melanoma where the objective response rate to anti-PD-1 monotherapy is ~30-35%. Overall, the data indicate a favorable benefit/risk profile for the evaluation of a combination of urelumab with nivolumab in this study since the availability of more effective therapies or combination of agents would be of great benefit to these patients with advanced cancer.

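### Do the Synopsis figures of about 260 subjects and 4.5 years need correcting because the cohort tables and Amendment 08 imply more?

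*Protocol*

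**What the plan says.** The Synopsis, under Number of Subjects, reads "Up to approximately 260 subjects will be dosed". It gives no derivation. Protocol Section 8.1 and SAP Section 5 size the dose levels and cohorts one by one and state no study total.

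The pieces that make up a total are these:

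- **Dose escalation.** Table 1 gives "n = approximately 6-18". The Synopsis sample-size text adds that "up to 12 subjects may be dosed at selected cohorts".
- **Two-stage expansion.** Table 4 (repeated as Table 3.1.6-1) lists seven such cohorts. Each has about 20 subjects in Stage 1, followed by "continued enrollment of up to approximately 20 additional subjects (total of 40 subjects per tumor type".
- **PD-L1-negative melanoma.** This is a single block: "Up to approximately 50 subjects at MTD or HAD". More may be enrolled to reach 50 evaluable.
- **Stage 2 gate.** At least 4 of 20 responses are required. With 0 to 3, as a general rule, "Stage 2 will not be enrolled for that tumor type".

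On time, the Synopsis expects about 3.1 years per subject and 4.5 years overall. The overall figure runs from the first subject's first visit to the required survival follow-up of the last subject enrolled. Protocol Section 3.1.4 sets survival follow-up at 3 years from first dose; the Synopsis and Table 5.1-3 treat 3 years as an upper limit. The PD-L1-negative melanoma block came in with Amendment 08, dated 22-Mar-2017.

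**The concern.** A reader who adds up the tables passes 260 by a wide margin, and both the total and the tables use ceiling language. The total is also close to what the tables would give with only the six expansion cohorts listed in SAP Table 5. That raises the suspicion that it was never raised when the later melanoma cohorts were added.

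The duration invites the same suspicion. Subjects who could not be dosed before late March 2017 and are to be followed for 3 years do not fit easily into 4.5 years if the trial began in 2014 or the first half of 2015.

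If 260 were a binding cap, cohorts that the protocol promises to open might have no room. If 4.5 years were a hard stop, follow-up of the last subjects might be cut short.

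**Working it through.** **Number of subjects: sum of the caps**

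- Two-stage cohorts: 7 × 40 = 280.
- PD-L1-negative melanoma: 50, so expansion is 280 + 50 = 330.
- Escalation: 18 (Table 1), or 24 if both levels go to 12.
- Sum: 330 + 18 = 348; 330 + 24 = 354.
- Gap to 260: 88 (88/348 = 25.3%) or 94 (94/354 = 26.6%).

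The roughly 18 PD-L1-negative subjects pooled from Cohort 2 in Section 8.1.2.2 had already been treated, so they are not added again.

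**Number of subjects: with the Stage 2 gate applied**

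Let k be the number of two-stage cohorts that enter Stage 2. The total is 7 × 20 + 50 + escalation + 20k, that is, 208 + 20k (escalation 18) or 214 + 20k (escalation 24).

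| k | Escalation 18 | Escalation 24 |
|---|---|---|
| 0 | 208 | 214 |
| 1 | 228 | 234 |
| 2 | 248 | 254 |
| 3 | 268 | 274 |
| 7 | 348 | 354 |

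Solving for 260 gives k = (260 − 214)/20 = 2.3 to (260 − 208)/20 = 2.6. So 260 accommodates two open Stage 2 cohorts, with 6 to 12 places left for extra PD-L1-negative subjects.

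**Is k of about 2 plausible?** Protocol Section 1.5 reports "Preliminary data in 138 patients treated with urelumab and nivolumab as of the clinical cutoff date of 30-Sep-2016", and "Twenty-five of 124 evaluable patients treated with the combination had objective responses". Of these responses, 23 were in 46 melanoma subjects, 1 was in SCCHN and 1 in NSCLC. Outside melanoma that is 25 − 23 = 2 responses among 124 − 46 = 78 evaluable subjects. Five of the seven two-stage cohorts are not melanoma (two NSCLC, SCCHN, DLBCL, FL), and none of them can have had more than one response by then, against the four required. The two two-stage melanoma cohorts remain as the likely candidates, which gives 248 to 254. Enrolment per cohort at that date is not reported, so this shows plausibility and does not prove it.

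**By actual accrual.** 138 + 50 = 188, leaving 260 − 188 = 72 places for all other accrual after 30-Sep-2016.

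**The competing explanation.** Six cohorts without the later melanoma additions give 6 × 40 + 18 = 258 or 6 × 40 + 24 = 264. This is about as close to 260 as k = 2, so the arithmetic cannot say which reading the authors had in mind.

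**Duration**

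- Per subject: (28 days + 3 × 365.25 days)/365.25 = 3.08 years, which reproduces the stated 3.1.
- Earliest end of 3 years for an Amendment 08 subject: 22-Mar-2017 + 3 years = 22-Mar-2020.
- First visit needed for a 4.5-year total: about 22-Sep-2015.
- First visit on the original protocol date, 10-Jun-2014: 2.78 + 3 = 5.78 years.
- First visit as late as 29-Jun-2015 (Revised Protocol 02): 1,728 days = 4.73 years, which is 84 days over.

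These figures allow no time to accrue the 50 subjects. The first-visit date is not in the documents. However, Protocol Table 4-1 and SAP Section 7.4.1 both provide for subjects enrolled before Revised Protocol 02 / Amendment 03, which points to a start before 29-Jun-2015.

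**The case for a change.** The best argument for a correction is that the Synopsis is the only place that gives a study total and a study length, so both should be right on their own terms. The wording of the total reads as a ceiling, and nothing in the protocol says that it assumes most Stage 2 cohorts stay closed. The gate is also soft: it is a general rule, delayed responses can reopen a cohort, and the PD-L1-negative block may exceed 50. Nothing therefore enforces 260. The duration conflicts more directly with the follow-up used to define it.

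Part of this stands. The basis for 260 is not stated, and the 4.5 years very probably was not refreshed for Amendment 08. Two qualifications apply to the duration. It is given as an expectation, and the Synopsis treats 3 years as an upper limit, so a last subject who dies or withdraws finishes sooner. Also, a provision for early enrollees does not by itself prove that there were any.

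What does not stand is that 260 is an arithmetic error. An overall ceiling below the sum of conditional ceilings is coherent, because that sum is reached only if every gate opens. Replacing 260 with about 350 and calling it a maximum would be no better. Extra PD-L1-negative subjects and alternate regimen C remain possible, so 350 is not a true maximum either.

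**Conclusion.** No change to the plan follows. The total of 260 is compatible with the Stage 2 rule if about two of seven cohorts go on, and the interim responses make that a reasonable expectation. The only gap is an unstated assumption, which a reader can reconstruct from the tables and Section 1.5. The duration is probably a clerical slip of about 0.23 to 1.28 years (4.73 − 4.5 to 5.78 − 4.5) before accrual time. That range assumes a first visit between 10-Jun-2014 and 29-Jun-2015 and a full 3 years of follow-up for an Amendment 08 subject.

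Neither figure drives anything else. The study tests no formal primary hypothesis. Precision statements and the 4-of-20 rule are set per cohort, at 20, 40 or 68 subjects. Response rates are reported by tumor type on the subjects actually treated. Survival follow-up runs from each subject's own first dose, so an outdated calendar total shortens nobody's follow-up, and the Kaplan-Meier analyses use whatever follow-up was observed. Restating the two lines would tidy the Synopsis and leave conduct, analysis and conclusions as they are.
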